9.1.1.3 Extension of Screening Period Window

A subject may have the Screening Period window extended by 2 weeks for the following reasons:

- Repetition of the Screening Period assessments (Section 9.1.1.1)
- Unexpected operational or logistic delays, or to meet the eligibility criteria
- Scheduling of ophthalmologic examination (Section 11.4.5)

9.1.2 Treatment Period

Treatment Period assessments are listed in Table 3-2.

The Treatment Period will last approximately 13 weeks. Study drug administration details are provided in Section 9.6.

9.1.3 Follow-up

The Safety Follow-up Visit is scheduled to occur 28 (\pm 7) days after the last dose of study drug. The Safety Follow-up Visit is not required for subjects who complete the Week 13 Visit and enroll in the open-label extension safety study, or who transition to a commercially available *CFTR* modulator regimen, within 28 days after the last dose of study drug.

9.1.4 Early Termination of Treatment

If a subject prematurely discontinues study treatment, an Early Termination of Treatment (ETT) Visit should be scheduled as soon as possible after the subject decides to terminate study treatment. Subjects who prematurely discontinue treatment will also be required to complete the Safety Follow-up Visit.

If the ETT Visit occurs 3 weeks or later following the last dose of study drug, then the ETT Visit will replace the Safety Follow-up Visit, and a separate Safety Follow-up Visit will not be required.

If a subject withdraws from the study and also withdraws consent or assent, no further assessments will be performed. Vertex may retain and continue to use any data and samples collected before such withdrawal of consent or assent.

Wearable devices must be returned to the site during the ETT Visit.

9.1.5 Lost to Follow-up

A subject will be considered lost to follow-up if both of the following occur:

- The subject misses 2 consecutive study visits (telemedicine contact or clinic visit) and is subsequently unable to be contacted by telephone (3 documented attempts by telephone within 2 weeks following the second missed visit)
- The subject does not respond within 2 weeks to a registered letter sent after the 3 attempted telephone contacts.

9.1.6 Completion of Study Participation

Completion of study participation for each individual subject is defined as 1 of the following:

- For subjects who complete the Treatment Period and enter an open-label extension safety study within 28 days of the Week 13 Visit: the Week 13 Visit
- For subjects who complete the Treatment Period and do not enter an open-label extension safety study within 28 days of the Week 13 Visit: the Safety Follow-up Visit
- For subjects who prematurely discontinue study drug treatment but do not withdraw consent (and assent, as applicable): the later of the ETT Visit or Safety Follow-up Visit (if required)
- For subjects who withdraw consent or assent: date of withdrawal of consent or assent, whichever is earlier (Section 9.9)

If subjects are lost to follow-up (Section 9.1.5), the date of completion of study participation will be defined as the date of the last contact.

The end of study is defined in Section 13.2.9.

9.1.7 Use of Remote Measures

Study visits must be performed in the clinic as specified in Table 3-1 and Table 3-2. A number of other contacts will be performed remotely via telemedicine contact. Under extenuating circumstances, certain remote measures may be implemented (e.g., due to safety concerns and/or local restrictions related to COVID-19 or other emerging events). Even under extenuating circumstances, the Screening (including initial consent), Day 1, Week 13, ETT, and Safety Follow-up visits must still be performed in the clinic.

The following remote measures may be implemented. Additional details can be found in the Study Reference Manual.

- Study drug may be shipped directly from the site to the subject, as applicable and as allowed per local regulations.
- Remote monitoring visits may be implemented, as applicable (including remote source data verification) and as allowed per local regulations.

9.2 Method of Assigning Subjects to Treatment Groups

This is an open-label study.

9.3 Rationale for Study Elements

9.3.1 Study Design

This open-label study will evaluate the effects of ELX/TEZ/IVA on cough and physical activity in CF subjects. Wearable technology will be used to measure cough frequency, daily physical

activity, [REDACTED] in a real-world setting. A 2-week baseline period will be used to establish baseline cough, activity, [REDACTED] prior to the first dose of study drug.

9.3.2 Study Population

This study will enroll CF subjects with F/MF genotypes, 12 years of age and older. ELX/TEZ/IVA is expected to provide clinical benefit to these subjects based on the results of a Phase 3 study (Study VX17-445-102), which demonstrated the efficacy and safety of ELX/TEZ/IVA in CF subjects ≥ 12 years of age who have F/MF genotypes.

9.3.3 Study Drug Dose

The dose of ELX/TEZ/IVA evaluated in the pivotal Phase 3 study in subjects with F/MF genotypes ≥ 12 years of age (ELX 200 mg qd/TEZ 100 mg qd/IVA 150 mg q12h) was generally safe and well tolerated and resulted in clinically meaningful improvements compared to placebo in endpoints including ppFEV₁ (LS mean treatment difference of 14.3 percentage points [$p < 0.0001$] for absolute change from baseline) and sweat chloride (LS mean treatment difference of -41.8 mmol/L [$p < 0.0001$] for absolute change from baseline) through 24 weeks. This dose of ELX/TEZ/IVA is approved in some regions for the treatment of CF and will be used for all subjects enrolled in this study.

9.3.4 Rationale for Study Assessments

The safety assessments are standard parameters for clinical studies in drug development.

The cough, physical activity, [REDACTED] will be performed using wearable technology. These measurements will help to inform on the effects of ELX/TEZ/IVA on cough, physical activity, [REDACTED] in a real-world setting.

Cough is one of the most common and burdensome symptoms of CF and negatively impacts quality of life. The measurement of cough frequency reduction in response to treatment with ELX/TEZ/IVA would be a clinically meaningful outcome measure. The cough monitoring system is a reliable, robust, and efficient tool for the objective measurement of cough frequency. Using mechanoacoustic measurements, cough counts can be obtained over a continuous 24-hour period.

Daily activity [REDACTED] reflect both the functional and physiological health of subjects. Use of a well-validated Class I actigraphy medical device would allow for the collection of quantifiable metrics around daily activity [REDACTED]. In conjunction with subject-reported data (activity and cough diary, [REDACTED]), the actigraphy data will enable the potential health economic impact of ELX/TEZ/IVA. Actigraphy devices are worn on the wrist and provide objective information on physical activity [REDACTED] habits in the patient's natural environment. The actigraphy device is a cost-effective and minimally invasive in-home alternative to other methods to measure these behaviors (e.g., polysomnography), and offers a level of accuracy and reliability that cannot be achieved through subjective patient reports.

9.4 Study Restrictions

Table 9-1 lists prohibited medications. A non-exhaustive list of study prohibitions and cautions for medication will be provided in the Study Reference Manual.

Table 9-1 Prohibited Medications

Medication	Timing of Restriction		Rationale
	Start of Restriction	End of Restriction	
Moderate and strong CYP3A inducers	None allowed within 14 days before the first dose of the study drug on Day 1	None allowed through completion of study participation	ELX, TEZ, and IVA are metabolized extensively via CYP3A4. Therefore, use of moderate and strong inducers and inhibitors of CYP3A, which have the potential to alter the exposure of ELX, TEZ, or IVA, are prohibited.
Moderate and strong CYP3A inhibitors (except ciprofloxacin) ^a	None allowed within 14 days before the first dose of the study drug on Day 1	None allowed through completion of study participation	
CFTR modulators (investigational or approved), except for study drugs	None allowed within 6 months before Day -14	None allowed until after the last dose of study drug	These agents may confound the results of this study.

CYP: cytochrome P450; ELX: elexacaftor; IVA: ivacaftor; TEZ: tezacaftor

^a Ciprofloxacin is not a moderate CYP3A inhibitor on the basis of results of a drug-drug interaction study conducted with IVA, a sensitive CYP3A substrate (Kalydeco [ivacaftor] US Package Insert).

9.5 Prior and Concomitant Medications

Information regarding prior and concomitant medications, including CF medications, other medications, and herbal and naturopathic remedies, will be collected from each subject's source documentation for medications taken within 56 days before the Screening Visit through completion of study participation, as defined in Section 9.1.6.

For subjects who are screened but are not subsequently enrolled, details of prior medication will be documented only in the subjects' source documents.

- Subjects should remain on a stable treatment regimen for their CF from 28 days before the Day 1 Visit through completion of study participation. Stable treatment regimen is defined as the current treatment regimen for CF that subjects have been following for at least 28 days before the Day 1 Visit. Subjects should not initiate long-term treatment with new medication from 28 days before the Day 1 Visit through completion of study participation. Guidelines for stable treatment regimens for CF are as follows:
 - o Subjects who are taking inhaled tobramycin or other chronically inhaled antibiotics should remain on that regimen throughout the study.
 - o Subjects who cycle onto and off of an inhaled antibiotic should continue on their prior schedule. The timing of the first dose of study drug on the Day 1 Visit should be synchronized as closely as possible (e.g., not more than ± 3 days) to the first day in the cycle onto the inhaled antibiotic.

- o Subjects who alternate between 2 different inhaled antibiotics should remain on the same cycling schedule during the study. The timing of the first dose of study drug on the Day 1 Visit should be synchronized as closely as possible (e.g., not more than ± 3 days) to the first day in the cycle onto 1 of the inhaled antibiotics.
- Subjects may receive doses of prednisone or prednisolone of up to 10 mg/day chronically, or up to 60 mg daily for up to 5 days.
- ELX may inhibit OATP1B1 and OATP1B3, which may increase the exposure of medicinal products that are substrates for these transporters. Substrates such as statins, glyburide, nateglinide, and repaglinide should be used with caution.
- IVA is a weak inhibitor of P-glycoprotein (P-gp). Administration of IVA may increase systemic exposure of medicinal products that are sensitive substrates of P-gp, which may increase or prolong their therapeutic effect and adverse reactions. Digoxin or other substrates of P-gp with a narrow therapeutic index, such as cyclosporine, everolimus, sirolimus, and tacrolimus, should be used with caution and appropriate monitoring.
- IVA may inhibit CYP2C9; therefore, during coadministration with warfarin, additional monitoring of the international normalized ratio is recommended. Other medicinal products that are CYP2C9 substrates for which exposure may be increased include glimepiride and glipizide; these should be used with caution.
- Information about bronchodilator use during the study will be collected and documented. Subjects who are using a bronchodilator should have their spirometry assessments performed according to the guidelines provided in Section 11.3.4.

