3 SCHEDULE OF ASSESSMENTS

Schedules of assessments are in Table 3-1 and Table 3-2.

Table 3-1 Study VX20-445-126: Screening

Event/Assessment	Screening Visit Day -42 to Day -15	Comments
Study visit	X	The Screening Visit must be performed in the clinic.
Informed consent (and assent, if applicable)	X	Electronic consent may be used, as applicable, if permitted by local regulations. If not permitted or if subject declines electronic consent, subjects will sign a paper consent form.
Demographics	X	Section 11.1
Medical history	X	Section 11.1
Medications review	X	Information regarding medications taken within 56 days before the Screening Visit will be collected (Section 9.5)
Height and weight	X	Measured with shoes off (Section 11.1)
Complete PE	X	Section 11.4.3
CF genotype	X	If the CFTR genotype result is not received before the first dose of study drug, a previous CFTR genotype laboratory report may be used to establish eligibility (Section 8.1) Subjects who have been enrolled and whose screening genotype does not confirm study eligibility must be discontinued from the study (Section 9.9).
FSH	X	Performed for any suspected menopausal female with at least 12 months of continuous spontaneous amenorrhea (Section 11.4.2)
Serum pregnancy (all female subjects)	X	Section 11.4.2
Serum chemistry (including creatine kinase)	X	
Hematology	X	
Adverse events	Continuous, from the date of informed consent through completion of study participation	Section 13.1; completion of study participation is defined in Section 9.1.6.

FSH: follicle stimulating hormone; PE: physical examination

Table 3-2 Study VX20-445-126: Baseline Period, Treatment Period, and Safety Follow-up Visit

Event/Assessment ^a	Baseline Period	Treatment Period						ETT Visit	Safety Follow-up Visit (28 ± 7 Days After Last Dose of Study Drug) ^b	Comments
	Day -14 to Day -1	Day 1	Weeks 2, 3, 5, 6, 7, 9, 10, 11	Week 4	Week 8	Week 12	Week 13			
Study visit		X					X (+6 days ^c)	X	X	Must be performed in the clinic.
Telemedicine contact	Day -14, Day -7 (+6 days ^c)		X (+6 days ^c)	X (+6 days ^c)	X (+6 days ^c)	X (+6 days ^c)				Assess subject's status, any AEs, concomitant medications, treatments, procedures, results of the urine pregnancy test (all female subjects), study drug count, and observe subject placement of cough device.
Safety, Efficacy, and Other Assessments										
Complete PE		X					X	X		Section 11.4.3

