Height and weight		X					X	X		Measured with shoes off. Height will only be collected for subjects ≤21 years of age on the date of informed consent (Section 11.1)

^a All assessments will be performed before dosing unless noted otherwise.

^b The Safety Follow-up Visit is not required for subjects who complete the Week 13 Visit and have enrolled in an open-label extension study, or who transition to a commercially available CFTR modulator regimen, within 28 days after the last dose of study drug.

^c The 7-day window begins on the first day of that week (e.g., at Week 2 the window begins on Day 8, at Week 3 the window begins on Day 15, etc.).

Table 3-2 Study VX20-445-126: Baseline Period, Treatment Period, and Safety Follow-up Visit

Event/Assessment ^a	Baseline Period	Treatment Period						ETT Visit	Safety Follow-up Visit (28 ± 7 Days After Last Dose of Study Drug) ^b	Comments
	Day -14 to Day -1	Day 1	Weeks 2, 3, 5, 6, 7, 9 10 11	Week 4	Week 8	Week 12	Week 13			
[Redacted]										
Pregnancy test (all female subjects)		Urine		Urine	Urine	Urine		Urine	Urine	During the Treatment Period, a urine pregnancy test will be performed with a home kit provided by the study site. Results will be reported to the site (Section 11.4.2).
Serum chemistry		X					X	X	X	Section 11.4.2
[Redacted]										

Table 3-2 Study VX20-445-126: Baseline Period, Treatment Period, and Safety Follow-up Visit

Event/Assessment ^a	Baseline Period	Treatment Period						ETT Visit	Safety Follow-up Visit (28 ± 7 Days After Last Dose of Study Drug) ^b	Comments
	Day -14 to Day -1	Day 1	Weeks 2, 3, 5, 6, 7, 9, 10, 11	Week 4	Week 8	Week 12	Week 13			
Cough measurements	Day -14, Day -7		X	X	X	X				Cough monitoring system will be used for a single day (defined by 24 continuous hours) at each time point (Section 11.2.1). Subjects will put the cough device on under direct observation at the time of contact between the subject and investigator or site personnel (i.e., in person or telemedicine contact).
Activity measurements	Continuous from Day -14 through Week 13 Visit									Wrist-worn actigraphy sensor will be worn 24 hours per day during the Baseline Period and Treatment Period (Section 11.2.2).
Adverse events	Continuous from date of informed consent through completion of study participation								Completion of study participation is defined in Section 9.1.6.	
Medications review	Continuous from date of informed consent through completion of study participation									

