9.3.1 Analysis of Primary Efficacy Variable

9.3.1.1 Definition of Variable

The primary endpoint is percent reduction from baseline in cough frequency (cough events per day) to the average of Week 8 through Week 12. Percent reduction from baseline will be calculated and expressed in percentage as $100\% \times (\text{baseline value} - \text{post-baseline value}) / \text{baseline value}$ (i.e., -relative change)

Cough frequency per day will be measured by a non-invasive, semi-automated, ambulatory cough monitoring system. The device will be used for a single day (defined by 24 continuous hours) at visits specified in Table 3-2 in CSP. The 24-hour assessment is considered valid if there are at least 10 cumulative hours of recording duration while awake, excluding any duration where the recording is identified as muted, flagged, or device not attached, and excluding any duration where the recording ended early.² For valid assessments, the cough frequency per day is the total number of cough events in the 24-hour period (excluding any duration where the recording is identified as muted, flagged, or device not attached, and excluding any duration where the recording ended early).

The baseline value is defined as the geometric mean of valid cough measurements prior to the first dose of study drug (e.g., Day -14 and Day -7). If one value is missing or invalid, the non-missing, valid value will be used. If the cough frequency is zero at a given visit, 0.5 will be added to ensure a non-zero number.

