9.3.1.2 Primary Analysis

The primary endpoint is the percent reduction from baseline in cough frequency (cough events per day) to the average of Week 8 through Week 12. The primary analysis will be based on a mixed-effects model for repeated measures (MMRM) with change from baseline at each post-baseline visit (Week 2 to Week 12) on the natural log scale (i.e., $\log(\text{post-baseline}) - \log(\text{baseline})$) as the dependent variable. Note that if cough frequency is zero at any visit, 0.5 will be added in order to ensure a non-zero number for appropriate natural log calculations. The model will include visit as a fixed effect and log baseline cough frequency as a covariate. The model will be estimated using restricted maximum likelihood. Denominator degrees of freedom for the F-test for fixed effects will be estimated using the Kenward-Roger approximation.³ An unstructured covariance structure will be used to model the within-subject errors. If the model estimation does not converge, a compound symmetry covariance structure will be used instead. Conditional on the observed data and covariates, missing data will be assumed to be missing at random; no additional imputation of missing data will be performed.

The primary result obtained from the model will be the estimated percent reduction in cough frequency from baseline to the average of Week 8 through Week 12 (defined as the average of Weeks 8, 9, 10, 11, 12). Percent reduction will be calculated as $100\% \times (1 - \text{exponential form of LS mean change at the average of Weeks 8 through 12 on the natural log scale from the above MMRM model})$. The 2-sided 95% confidence intervals will be provided. Furthermore, the estimated percent reduction at each post-baseline week will also be provided. The estimated percent reduction at each post-baseline week up to Week 12 will be plotted.

The geometric mean and geometric SD of the raw values at baseline and each post-baseline visit up to Week 12 will also be summarized. In addition, daytime and overnight cough frequency per hour will be summarized in a similar way. If the daytime or overnight cough frequency per hour is zero at a given visit, 0.5/24 will be added to ensure a non-zero number.

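### Does aligning Day 1 with the start of an inhaled-antibiotic cycle distort the Week 8-12 cough reduction enough to need an added analysis?

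*Protocol*

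**What the plan says.** Protocol 9.5 keeps on/off users of inhaled antibiotics on their existing schedule ("Subjects who cycle onto and off of an inhaled antibiotic should continue on their prior schedule"). The first dose of study drug "should be synchronized as closely as possible", with 3 days either way given as an example, "to the first day in the cycle onto the inhaled antibiotic". Subjects who alternate between two inhaled antibiotics get a parallel rule.

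Cough is recorded for 24 hours at Day -14 and Day -7, and weekly from Week 2 to Week 12. Footnote c of Protocol Table 3-2 sets the contact windows: "The 7-day window begins on the first day of that week".

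SAP 9.3.1.1 defines baseline: "The baseline value is defined as the geometric mean of valid cough measurements prior to the first dose of study drug". SAP 9.3.1.2 specifies the MMRM: "The model will include visit as a fixed effect and log baseline cough frequency as a covariate". The endpoint is "defined as the average of Weeks 8, 9, 10, 11, 12", with target days 50, 57, 64, 71 and 78 in SAP Appendix A. The same section plans an estimate and a plot for every post-baseline week.

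Inhaled antibiotics appear in SAP 9.2.2 as prior use, yes or no. SAP 9.2.4 tabulates medications by name and class. No visible text flags cyclers or classifies recordings by phase. Part of the SAP between 9.3.2 and 9.4 is redacted, so this describes visible text only.

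**The concern.** In a single-arm pre-post comparison, anything that changes systematically between baseline and endpoint enters the estimate. Left to chance, cycle phase would vary from subject to subject and largely average out. The synchronisation rule lines it up instead: cyclers with the same cycle length share the same contrast, typically OFF at baseline and ON for some of Weeks 8-12. If cough is lower when ON, the reduction credited to study drug is too large. If cough is higher when ON, it is too small. Visit and log baseline cannot remove such a shift, and prior use as yes/no does not separate cyclers from continuous or alternating users. A reader of the report could not tell whether phase contributed.

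**Working it through.** **1. The plan's own precision.** Inputs from Protocol 12.1: SD 1 on the log scale and 100 subjects with 20% missing, so n = 80. Half-width = 1.96/√80 = 0.219. Limits are 1 − ratio × exp(±0.219), which give 12.9-43.8%, 25.3-51.8% and 37.8-59.8% for observed reductions of 30%, 40% and 50%. These round to Table 12-1.

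**2. Which recordings are ON.** The documents give no cycle length, so the cycles below are assumptions (days ON/days OFF). Let the ON phase start s days after Day 1, with s from −3 to +3 and no Day 0. A post-dose day d is ON if (d − 1 − s) modulo cycle length is below the ON length. For 28/28 at s = 0, Day 50 gives 49 (OFF), while Days 57, 64, 71 and 78 give 0, 7, 14 and 21 (ON), so 4 of 5 are ON.

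| Assumed cycle | ON of 5, target days | ON of 5, any day in the 7-day contact windows |
|---|---|---|
| 28/28 | 3-4 | 3-5 |
| 21/21 | 2-3 | 1-3 |
| 14/14 | 2 | 1-4 |
| 28/56 | 0 | 0-1 |

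Both baseline target days are OFF at every shift for 28/28, 21/21 and 28/56. Under 14/14, Day -14 is ON at s = +1 to +3. A late Day -7 recording (Days -3 to -1) is ON at s = −3. SAP Appendix A also accepts Day -14 recordings back to Day -28, and some of those would be ON under shorter cycles. These exceptions shrink the contrast.

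**3. Possible size.** Log shift = k × f × ln(r), where k is the share of the five endpoint recordings that are ON, f the share of cyclers, and r the ON/OFF cough ratio, with baseline fully OFF. The values of f and r are assumptions (10-40%; 0.7-0.9 or 1.1-1.3).

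| f | r | k | Log shift | True 40% reads | Share of half-width |
|---|---|---|---|---|---|
| 0.10 | 0.90 | 0.6 | −0.006 | 40.4% | 0.03 |
| 0.20 | 0.80 | 0.8 | −0.036 | 42.1% | 0.16 |
| 0.40 | 0.70 | 0.8 | −0.114 | 46.5% | 0.52 |
| 0.40 | 0.70 | 1.0 | −0.143 | 48.0% | 0.65 |
| 0.40 | 1.30 | 0.8 | +0.084 | 34.7% | 0.38 |
| any | any | 0 | 0 | 40.0% | 0 |

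With no drug effect, the mid case gives an apparent reduction of 1 − exp(−0.036) = 3.5%, and the most extreme row 1 − exp(−0.143) = 13.3%. Neither reaches the 30-50% for which the study is sized. In that extreme row an observed 30% would correspond to 1 − 0.7/0.867 = 19.3%, with a lower limit of 1 − 0.807 × 1.245 = −0.5%. This needs every assumption at its limit together with the smallest tabulated reduction.

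**4. What an added analysis would show.** Compare the model without cyclers with the primary result, using SE = √(1/n_sub − 1/80), k = 0.8 and a common drug effect:

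- f = 0.10, r = 0.90: shift 0.008, SE 0.037, power 6%.
- f = 0.20, r = 0.80: shift 0.036, SE 0.056, power 10%.
- f = 0.40, r = 0.70: shift 0.114, SE 0.091, power 24%.

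At an observed 40% reduction the interval widens from (25%, 52%) at n = 80 to (23%, 53%) at n = 64 and (20%, 55%) at n = 48. Removing every synchronised contrast would mean leaving out alternators as well, which costs further subjects.

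**The case for a change.** The best case for acting is that the protocol itself treats cycle timing as worth controlling at Day 1, and the SAP does not carry that into the analysis. A baseline category for the antibiotic pattern and one repeat of an existing model cost little. The planned weekly estimates do not fill the gap. They pool everyone, and no week is OFF under all four assumed cycles (at exact synchronisation: Weeks 5-8 for 28/28; 4-6 and 10-12 for 21/21; 3-4, 7-8 and 11-12 for 14/14; 5-12 for 28/56). A later check may also be harder than it looks. The documents do not say that each ON/OFF cycle is dated, and SAP Appendix C sets a missing start day to the first of the month, which could misplace a phase.

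All of this is accurate, and a baseline flag would be a reasonable courtesy to readers. It does not show that the plan needs the change. The comparison with and without cyclers is too weak to reveal the effect and concerns a somewhat different population. A summary of ON and OFF recordings within cyclers is confounded with time on drug, because synchronisation makes phase nearly track visit. The protocol collects CF medications from 56 days before Screening to the end of participation, so analysts have a starting point if the question arises.

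**Conclusion.** No change follows. The phase contrast is a real feature of the design: subjects stay on their usual regimen from a common starting phase, which is a fair trade-off in a single-arm study of this kind. The documents settle neither the sign nor the size of its effect on cough. Under the assumed ranges the shift runs from zero to 0.65 of the planned half-width, with 0.16 in the mid case, and the larger values need many cyclers, a strong phase effect and nearly all endpoint recordings ON at once. The study estimates a reduction with a confidence interval and sets no test or decision threshold on it. The supportive analyses would leave the primary estimate untouched and could not reliably show whether phase contributed. The conclusion rests on the visible SAP text, the assumed cycles, and the planning values of SD 1 and n = 80. It makes no comment on how antibiotics should be managed.
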